6.5.2 Prohibited Medicines

As stated for the exclusion criteria in Section 5.3.2, subjects must not have had chemotherapy, radiotherapy involving more than 30% of the bone marrow (other than palliative bone directed radiotherapy as described in Section 6.5.1) within 21 days before the start of trial treatment, and anticancer treatment with antibody, major surgery, or received another investigational agent within 28 days before the start of trial treatment.

The following treatments must not be administered during the trial:

- Immunotherapy, immunosuppressive drugs (eg, chemotherapy or systemic corticosteroids except for short-term treatment of allergic reactions, endocrine replacement therapy at low dose prednisone [≤ 10 mg daily] or equivalent, or for the treatment of irAEs or other appropriate short-term steroid use), or other experimental pharmaceutical products. Short-term administration of systemic steroid or other immunosuppressant such as infliximab or mycophenolate (ie, for allergic reactions or the management of irAEs) is allowed. Steroids with no or minimal systemic effect (topical, inhalation) are allowed.
- Adefovir.
- Prophylactic use of corticosteroids for infusion-related reactions is prohibited.
- Any live vaccine therapies for the prevention of infectious disease. Administration of inactivated vaccines is allowed (eg, inactivated influenza vaccines).
- Blood transfusions and erythroid growth factors are not allowed during the 21-day DLT window during the escalation part.

CONFIDENTIAL 83/167

If the administration of a non-permitted concomitant drug becomes necessary during the trial, the subject will be withdrawn from trial treatment (the Medical Monitor may be contacted to discuss whether the IMP must be discontinued).

Medications other than those specifically excluded in this trial (as outlined in this section) may be administered for the management of symptoms associated with the administration of MSB0011359C as required. These might include analgesics, antiemetics, antihistamines, diuretics, anti-anxiety medications, and medication for pain management, including narcotic agents.

Any additional concomitant therapy that becomes necessary during the trial and any change to concomitant drugs must be recorded in the corresponding section of the eCRF, noting the name, dose, duration, and indication of each drug.

6.5.3 Other Interventions

The following nondrug therapies must not be administered during the trial (and within 28 days before the start of trial treatment):

- Major surgery (excluding prior diagnostic biopsy).
- Herbal remedies with immunostimulating properties (eg, mistletoe extract) or known to potentially interfere with major organ function (eg, hypericin).
- Subjects should not abuse alcohol or other drugs during the trial.

6.5.4 Special Precautions

For subjects enrolled in the dose escalation part of the trial, in-house observation in a hospitalized setting for at least 24 hours will occur for the first 2 doses administered to each subject. To facilitate PK and colors, subjects may remain in-house through an additional 24 hours if necessary. A nurse or physician will communicate with the first subject of each cohort after the first treatment to assess for any side effects on or after Day 5 but before enrolling a subsequent subject. Thereafter, within each cohort, 48 hours must pass before a new subject can initiate dosing.

In the expansion part of the trial, there is no in-house observation and no waiting period between subjects.

At all times during MSB0011359C treatment, immediate emergency treatment of an infusion-related reaction or a severe hypersensitivity reaction according to institutional standards must be assured. In order to treat possible anaphylactic reactions, for instance, dexamethasone 10 mg and epinephrine in a 1:1000 dilution or equivalents should always be available along with equipment for assisted ventilation.

CONFIDENTIAL 84/167

Infusion of MSB0011359C will be stopped in case of Grade ≥ 2 hypersensitivity, inflammatory response, or anaphylactic reaction. The treatment recommendations for infusion-related reactions and severe hypersensitivity reactions according to the NCI are outlined in Sections 6.5.4.1 and 6.5.4.2, respectively.

Investigators should also monitor subjects closely for potential irAEs, which may become manifest after several weeks of treatment. Such events may consist of persistent rash, diarrhea and colitis, autoimmune hepatitis, arthritis, glomerulonephritis, cardiomyopathy, or uveitis and other inflammatory eye conditions. The spectrum of hypothetical irAEs also includes formation of auto-antibodies like ANAs.

6.5.4.1 Infusion-related Reactions

- A. Symptoms:
 - Fever
 - Chills
 - Rigors
 - Diaphoresis
 - Headache.
- B. Management (see Table 4)

N/N

Table 4 Treatment Modification for Symptoms of Infusion-related Reactions Caused by MSB0011359C

NCI-CTCAE Grade	Treatment Modification for MSB0011359C
Grade 1 – mild Mild transient reaction; infusion interruption not indicated; intervention not indicated.	 Decrease the MSB0011359C infusion rate by 50% and monitor closely for any worsening. The total infusion time for MSB0011359C should not exceed 120 minutes.
Grade 2 – moderate • Therapy or infusion interruption indicated but responds promptly to symptomatic treatment (eg, antihistamines, NSAIDs, narcotics, IV fluids); prophylactic medications indicated for ≤ 24 hours.	 Stop MSB0011359C infusion. Resume infusion at 50% of previous rate once infusion-related reaction has resolved or decreased to at least Grade 1 in severity, and monitor closely for any worsening.
 Grade 3 or Grade 4 – severe or life-threatening Grade 3: Prolonged (eg, not rapidly responsive to symptomatic medication and/or brief interruption of infusion); recurrence of symptoms following initial improvement; hospitalization indicated for clinical sequelae. Grade 4: Life-threatening consequences; urgent intervention indicated. 	 Stop the MSB0011359C infusion immediately and disconnect infusion tubing from the subject. Subjects have to be withdrawn immediately from MSB0011359C treatment and must not receive any further MSB0011359C treatment.

IV=intravenous; NCI-CTCAE=National Cancer Institute-Common Terminology Criteria for Adverse Event; NSAIDs=nonsteroidal anti-inflammatory drugs.

Additional Modifications for Subjects with Grade 2 Infusion-related Reactions

If, in the event of a Grade 2 infusion-related reaction that does not improve or worsens after implementation of the modifications indicated in Table 4 (including reducing the infusion rate by 50%), the Investigator may consider treatment with corticosteroids and the infusion of IMP should be stopped for that day. At the next infusion, the Investigator may consider the addition of H2-blocker antihistamines (eg, famotidine or ranitidine), in addition to premedication, for select subjects. However, prophylactic steroids are NOT permitted. If the subject has a second infusion-related reaction Grade ≥ 2 on the slower infusion rate, with or without the addition of further medication to premedication, the infusion should be stopped and the subject removed from MSB0011359C treatment.

6.5.4.2 Severe Hypersensitivity Reactions and Flu-like Symptoms

If a hypersensitivity reaction occurs, the subject must be treated according to the best available medical practice. A complete guideline for the emergency treatment of anaphylactic reactions according to the Working Group of the Resuscitation Council (United Kingdom) and can be found at https://www.resus.org.uk/pages/reaction.pdf. Subjects should be instructed to report any delayed reactions to the Investigator immediately.

CONFIDENTIAL INFORMATION

A. Symptoms

- Impaired airway
- Decreased oxygen saturation (< 92%)
- Confusion
- Lethargy
- Hypotension
- Pale/clammy skin
- Cyanosis.

B. Management

- 1. Epinephrine injection and intravenous dexamethasone.
- 2. Patient should be placed on cardiac, blood pressure, heart rate, and oxygen saturation monitor immediately.
- 3. Alert intensive care unit for possible transfer if required.

For prophylaxis of flu-like symptoms, an NSAID, eg, ibuprofen 400 mg or comparable NSAID dose, may be administered 2 hours before and 8 hours after the start of each dose of MSB0011359C IV infusion except for the DLT period (for subjects who experienced a flu-like syndrome in the DLT assessment period, prophylactic use of an NSAID at the next dose is allowed).

6.5.4.3 Immune-related Adverse Events

Since inhibition of PD-L1 stimulates the immune system, irAEs may occur. Treatment of irAEs is mainly dependent upon severity (NCI-CTCAE grade):

- Grade 1 to 2: Treat symptomatically or with moderate dose steroids, more frequent monitoring.
- Grade 1 to 2 (persistent): Manage similar to high grade AE (Grade 3 to 4).
- Grade 3 to 4: Treat with high dose corticosteroids.

Treatment of irAEs should follow guidelines set forth in Table 5.

Table 5 Management of Immune-Related Adverse Events

Gastrointestinal irAEs		
Severity of Diarrhea/Colitis (NCI-CTCAE v4.03)	Management	Follow-up
Grade 1 Diarrhea: < 4 stools/day over Baseline	Continue MSB0011359C therapy	Close monitoring for worsening symptoms

CONFIDENTIAL INFORMATION

Colitis: asymptomatic	Symptomatic treatment (eg, loperamide)	Educate subject to report worsening immediately If worsens: Treat as Grade 2 or 3/4
Grade 2 Diarrhea: 4 to 6 stools per day over Baseline; IV fluids indicated < 24 hours; not interfering with ADL Colitis: abdominal pain; blood in stool	Delay MSB0011359C therapy Symptomatic treatment	If improves to Grade 1: Resume MSB0011359C therapy If persists > 5 to 7 days or recur: 0.5 to 1 mg/kg/day methylprednisolone or equivalent When symptoms improve to Grade 1, taper steroids over at least 1 month, consider prophylactic antibiotics for opportunistic infections, and resume MSB0011359C therapy per protocol. If worsens or persists > 3 to 5 days with oral steroids: Treat as Grade 3 to 4
Grade 3 to 4 Diarrhea (Grade 3): ≥ 7 stools per day over Baseline; incontinence; IV fluids ≥ 24 hours; interfering with ADL Colitis (Grade 3): severe abdominal pain, medical intervention indicated, peritoneal signs Grade 4: life-threatening, perforation	Discontinue MSB0011359C therapy per protocol 1 to 2 mg/kg/day methylprednisolone IV or equivalent Add prophylactic antibiotics for opportunistic infections Consider lower endoscopy	If improves: Continue steroids until Grade 1, then taper over at least 1 month If persists > 3 to 5 days, or recurs after improvement: Add infliximab 5 mg/kg (if no contraindication), Note: Infliximab should not be used in cases of perforation or sepsis Permanently discontinue IMP
	Dermatological irAEs	S
Grade of Rash (NCI-CTCAE v4.03)	Management	Follow-up
Grade 1 to 2 Covering ≤ 30% body surface area	Symptomatic therapy (eg, antihistamines, topical steroids) Continue MSB0011359C therapy	If persists > 1 to 2 weeks or recurs: Consider skin biopsy Delay MSB0011359C therapy Consider 0.5 to 1 mg/kg/day methylprednisolone IV or oral equivalent. Once improving, taper steroids over at least 1 month, consider prophylactic antibiotics for opportunistic infections, and resume MSB0011359C therapy If worsens: Treat as Grade 3 to 4
Grade 3 to 4 Covering > 30% body surface area; life threatening consequences	Delay or discontinue MSB0011359C therapy Consider skin biopsy Dermatology consult	If improves to Grade 1: Taper steroids over at least 1 month and add prophylactic antibiotics for opportunistic infections

CONFIDENTIAL INFORMATION

	1 to 2 mg/kg/day methylprednisolone IV or IV equivalent	Resume MSB0011359C therapy (except in cases of Toxic Epidermal Necrolysis or Stevens-Johnson Syndrome)		
	Pulmonary irAEs			
Grade of Pneumonitis (NCI-CTCAE v4.03)	Management	Follow-up		
Grade 1 Radiographic changes only	Consider delay of MSB0011359C therapy Monitor for symptoms every 2 to 3 days Consider Pulmonary and Infectious Disease consults	Re-image at least every 3 weeks If worsens: Treat as Grade 2 or Grade 3 to 4		
Grade 2 Mild to moderate new symptoms	Delay MSB0011359C therapy Pulmonary and Infectious Disease consults Monitor symptoms daily, consider hospitalization 1 mg/kg/day methyl-prednisolone IV or oral equivalent Consider bronchoscopy, lung biopsy	Re-image every 1 to 3 days If improves: When symptoms return to near Baseline, taper steroids over at least 1 month and then resume MSB0011359C therapy and consider prophylactic antibiotics If not improving after 2 weeks or worsening: Treat as Grade 3 to 4 Permanently discontinue IMP		
Grade 3 to 4 Severe new symptoms; New/worsening hypoxia; life-threatening	Discontinue MSB0011359C therapy Hospitalize Pulmonary and Infectious Disease consults 2 to 4 mg/kg/day methylprednisolone IV or IV equivalent Add prophylactic antibiotics for opportunistic infections Consider bronchoscopy, lung biopsy	If improves to Baseline: Taper steroids over at least 6 weeks If not improving after 48 hours or worsening: Add additional immunosuppression (eg, infliximab, cyclophosphamide, IV immunoglobulin, or mycophenolate mofetil) Permanently discontinue IMP		
Hepatic irAEs				
Grade of Liver Test Elevation (NCI-CTCAE v4.03)	Management	Follow-up		
Grade 1 Grade 1 AST or ALT > ULN to 3.0 x ULN and/or total bilirubin > ULN to 1.5 x ULN	Continue MSB0011359C therapy	Continue liver function monitoring If worsens: Treat as Grade 2 or 3 to 4		

CONFIDENTIAL INFORMATION

Grade 2 AST or ALT > 3.0 to \leq 5 x ULN and/or total bilirubin > 1.5 to \leq 3 x ULN	Delay MSB0011359C therapy Increase frequency of monitoring to every 3 days	If returns to Baseline: Resume routine monitoring, resume MSB0011359C therapy If elevations persist > 5 to 7 days or worsen: 0.5 to 1 mg/kg/day methylprednisolone or oral equivalent and when LFT returns to Grade 1 or Baseline, taper steroids over at least 1 month, consider prophylactic antibiotics for opportunistic infections, and resume MSB0011359C therapy
Grade 3 to 4 AST or ALT > 5 x ULN and/or total bilirubin > 3 x ULN	Discontinue MSB0011359C therapy Increase frequency of monitoring to every 1 to 2 days 1 to 2 mg/kg/day methylprednisolone IV or IV equivalent Add prophylactic antibiotics for opportunistic infections Consult gastroenterologist Consider obtaining MRI/CT scan of liver and liver biopsy if clinically warranted	If returns to Grade 2: Taper steroids over at least 1 month If does not improve in > 3 to 5 days, worsens or rebounds: Add mycophenolate mofetil 1 gram (g) twice daily If no response within an additional 3 to 5 days, consider other immunosuppressants per local guidelines Permanently discontinue IMP
	Cardiac irAEs	
Myocarditis	Management	Follow-up
	CCI	CCI

CONFIDENTIAL INFORMATION

Guideline based supportive treatment as appropriate as per cardiology consult. ^a Methylprednisolone 1 to 2 mg/kg/day. Guideline based supportive treatment as appropriate as per cardiology consult. ^a If no improvement or worsening, consider additional immunosuppressants (eg, azathioprine, cyclosporine A).
--

a Local guidelines, or eg. European Society of Cardiology or American Heart Association guidelines

European Society of Cardiology guidelines website: https://www.escardio.org/Guidelines/Clinical-Practice-Guidelines American Heart Association guidelines website:

 $http://professional\ heart.org/professional/Guidelines Statements/search results.jsp? q=\&y=\&t=1001$

Endocrine ir AEs

Enquel me n AES			
Endocrine Disorder	Management	Follow-up	
Asymptomatic TSH abnormality	Continue MSB0011359C therapy If TSH < 0.5 x LLN, or TSH > 2 x ULN, or consistently out of range in 2 subsequent measurements: include free T4 at subsequent cycles as clinically indicated; consider endocrinology consult		
Symptomatic endocrinopathy	Evaluate endocrine function Consider pituitary scan Symptomatic with abnormal laboratory/pituitary scan: Delay MSB0011359C therapy 1 to 2 mg/kg/day methylprednisolone IV or by mouth equivalent Initiate appropriate hormone therapy No abnormal laboratory/ pituitary MRI scan but symptoms persist: Repeat laboratories in 1 to 3 weeks/MRI in 1 month	If improves (with or without hormone replacement): Taper steroids over at least 1 month and consider prophylactic antibiotics for opportunistic infections Resume MSB0011359C therapy Subjects with adrenal insufficiency may need to continue steroids with mineralocorticoid component	
Suspicion of adrenal crisis (eg, severe dehydration, hypotension, shock out of proportion to current illness)	Delay or discontinue MSB0011359C therapy Rule out sepsis Stress dose of IV steroids with mineralocorticoid activity IV fluids Consult endocrinologist If adrenal crisis ruled out, then treat as above for symptomatic endocrinopathy		

ADL=activities of daily living; ALT=alanine aminotransferase; AST=aspartate aminotransferase; CT=computed tomography; irAE=immune-related adverse event; IMP=investigational medicinal product; IV=intravenous; LFT=liver function test; LLN=lower limit of normal; MRI=magnetic resonance imaging; NCI-CTCAE=National Cancer Institute-Common Terminology Criteria for Adverse Events; T4=thyroxine; TSH=thyroid stimulating hormone; ULN=upper limit of normal.

> CONFIDENTIAL INFORMATION

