3.4.2 Immune-related Adverse Events/Autoimmune Disorders

Immune-related AEs/autoimmune disorders are events that are related to the pharmacology of checkpoint inhibitors and can be explained by an immune-phenomenon after other etiologies have been ruled out. Relevant clinical safety experience has been generated with the parent anti-PD-L1 avelumab antibody.

- As of 05 November 2014, a cumulative review revealed 56 cases of potential irAEs out of 480 subjects (11.7%) treated in the expansion part of trial EMR100070-001 and 4 cases out of 50 subjects (8.0%) treated in the dose-escalation part of trial EMR100070-001. A customized Medical Dictionary for Regulatory Activities (MedDRA) query was used for data retrieval from the clinical database with predefined preferred terms of potential irAEs.
- Of 69 potential irAEs reported, 13 were SAEs (18.8%) and 56 were nonserious AEs (81.1%). In the majority of the cases, there was a plausible temporal association between the event onset and the drug administration. Of these 69 events, 46 events (66.7%) were assessed as treatment-related by the Investigator and 23 events (33.3%) were assessed as not treatment-related by the Investigator.
- Twenty-six events were assessed as Grade 1, 29 events as Grade 2, 11 events as Grade 3, 2 events as Grade 4, and 1 event (pneumonitis) as Grade 5 (note: 2 more events of autoimmune hepatitis had a fatal outcome; however, they were assessed as Grade 3 with a subsequent fatal liver failure).
- Based on the irAE cases that have been observed with avelumab, all trial investigators will be trained to be made aware of the frequency and severity of the observed events and to proactively administer steroid treatment for any suspicion of irAEs.

CONFIDENTIAL 56/167

Based on clinical experience with avelumab and with other agents blocking the PD-1/PD-L1 pathway, irAEs/autoimmune disorders are an important identified risk and AESI for MSB0011359C. Risk management measures similar to the lead program include:

- Instructions for trial treatment discontinuation or interruption in case of irAEs/autoimmune disorders (see Section 6.5.4.3).
- Guidance for the medical management of irAEs/autoimmune disorders including specific guidance with regard to the affected organ/body system (see Section 6.5.4.3).

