- irAEs/autoimmune disorders (any grade) are considered as AESIs requiring expedited reporting from the Investigator to the Sponsor. For nonserious AESIs, an AESI Report Form has to be completed; for serious events, an SAE Report Form has to be used.
- Regular laboratory tests on parameters indicative for autoimmune disorders, such as thyroid stimulating hormone (TSH), will be performed as detailed in the Schedules of Assessments (see Table 1 and Table 2).
- To help monitor for autoimmune effects, baseline ophthalmology examination including slit lamp inclusive of the anterior segment and including visual acuity. If clinically relevant eye signs or symptoms occur during the trial, then an appropriate ophthalmology examination should be obtained within 2 days including slit lamp evaluation inclusive of the anterior segment and with visual acuity.

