16.2.3.2 Immune-Related Adverse Events

Immune-related adverse events (irAEs) will be identified programmatically. AEs which satisfy all of the following criteria will be flagged as immune-related:

- 1) The AE preferred term matches a preferred term on the list of pre-selected MedDRA terms.
- 2) The AE onset or worsening occurs after the first study drug administration and no more than 90 days after last dose, death or the earliest date of subsequent anticancer therapy minus 1 day, whichever occurs first.
- 3) On the AE eCRF page, the question "Were Corticosteroids, Immunosuppresants, or hormonal therapy (e.g. Thyroid) applied?" has the answer "Yes" selected.
- 4) On the imAE eCRF page, either:
 - a. The question "Does any of the following provide a clear etiology for the event?" has the answer "No" selected, indicating that the AE is not attributable to underlying cancer disease/PD, prior or concomitant medications/procedures, nor another medical condition such as an infection or pre-existing disease.

OR

b. The imAE eCRF indicates that a biopsy was performed and the question "Is the histopathology/biopsy consistent with an immune-mediated event?" has the answer "Yes" selected.

In the case that criteria (1) through (3) are met, and entries for condition (4) are missing, the following rules will be applied:

- If the answer to "Does any of the following provide a clear etiology for the event?" (4a) is missing, the event will be considered as irAE (irrespective of biopsy results).
- If the answer to "Is the histopathology/biopsy consistent with an immune-mediated event?" (4b) is missing, or if no biopsy was performed, and condition (4a) is not satisfied (i.e. "Yes" is selected as the answer to the question "Does any of the following provide a clear etiology for the event?"), the event will be considered as a non-irAE.

PTs will be compiled into categories: Immune-mediated rash, Immune-mediated colitis, Immune-mediated pneumonitis, Immune-related hepatitis, Immune-related nephritis and renal

dysfunction, Immune-mediated endocrinopathies (Adrenal insufficiency, Hypogonadism, Pituitary dysfunction, Type 1 Diabetes Mellitus, Thyroid disorders), Other immune-related adverse events (GVHD, Myasthenic syndrome, Myocarditis, Myositis, Neurologic events, Other, Pancreatitis, Uveitis, Vasculitis).

The overall summary of immune-related AEs (irTEAE) will include the following categories:

- Any irAEs
- irAEs by the worst grade
- Related irAEs

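### The SAP counts an adverse event as immune-related only if a corticosteroid, immunosuppressant or hormone was given, so low-grade irAEs managed without these drugs drop out of the irAE summaries

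*Protocol*

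**What the plan says.** SAP 16.2.3.2 sets the rule: "AEs which satisfy all of the following criteria will be flagged as immune-related". In summary, the four criteria are:

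1. The preferred term is on a pre-selected list.
2. Onset or worsening falls after the first dose and no later than 90 days after the last dose, or earlier if death or new anticancer therapy comes first.
3. The eCRF question "Were Corticosteroids, Immunosuppresants, or hormonal therapy (e.g. Thyroid) applied" is answered yes.
4. Either no other clear etiology is recorded (4a), or a biopsy supports an immune-mediated event (4b).

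The missing-data rules open with "In the case that criteria (1) through (3) are met, and entries for condition (4) are missing", so they apply only after criterion 3 is met. The outputs include any irAE, "irAEs by the worst grade", and related, serious and discontinuation-related irAEs. SAP 15.4 tabulates irAEs by ADA and nAb status. SAP 16.1 describes AESIs, irAEs among them, as found from a list of preferred terms, and names no treatment condition.

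Protocol 3.4.2 defines irAEs by cause once other explanations are excluded, and states "irAEs/autoimmune disorders (any grade) are considered as AESIs requiring expedited reporting from the Investigator to the Sponsor". Section 7.4.1.1.4 makes any suspected irAE an AESI. Neither section makes treatment a condition. Section 6.5.4.3 gives the general rule "Grade 1 to 2: Treat symptomatically or with moderate dose steroids, more frequent monitoring", and Table 5 adds detail by organ. For a Grade 1 liver elevation, for example, the follow-up is "Continue liver function monitoring If worsens: Treat as Grade 2 or 3 to 4".

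**The concern.** Under the protocol, whether a patient receives one of these drugs depends largely on grade. Making the drug a condition for the irAE flag therefore makes inclusion in the irAE tables depend on grade. A site that follows Table 5 exactly can report an event that the protocol regards as an irAE and that the SAP cannot count as one.

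Protocol 3.4 names irAEs as an important risk. A reader of these tables will take the first row as how often irAEs occurred and the grade rows as how severe they were, and both would be distorted in a known direction. The irAE comparison by ADA and nAb status would rest on the same reduced set of events. The result would also not be comparable with the parent-antibody experience in Protocol 3.4.2, which came from a preferred-term query with no stated treatment condition.

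**Working it through.** The plan gives no figure to reproduce. The check is to run the SAP rule against each low-grade row of Table 5.

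| Table 5 row | Initial management | Criterion 3 if Table 5 is followed |
|---|---|---|
| Diarrhea/colitis, Grade 1 | Symptomatic | Not met |
| Diarrhea/colitis, Grade 2 | Symptomatic; steroid if it lasts beyond 5 to 7 days or recurs | Met only in those cases |
| Rash, Grade 1 to 2 | Symptomatic; antihistamine or topical steroid as examples | Depends on how the site answers for topical use |
| Pneumonitis, Grade 1 | Monitoring | Not met |
| Pneumonitis, Grade 2 | Methylprednisolone from the start | Met |
| Liver tests, Grade 1 | Monitoring | Not met |
| Liver tests, Grade 2 | Closer monitoring; steroid if it lasts beyond 5 to 7 days or worsens | Met only in those cases |
| Asymptomatic TSH abnormality (ungraded) | Monitoring, possible consult | Not met |

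Of the 7 graded rows, 5 have no steroid in initial management, 1 has a topical steroid as an example only, and 1 has a systemic steroid at once.

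Two features of the rule follow from its logic:

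- A biopsy that satisfies 4b does not rescue an event that fails criterion 3.
- A blank answer to criterion 3 has no fallback, whereas a blank 4a counts the event as an irAE once criteria 1 to 3 are met.

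To illustrate possible size, Protocol 3.4.2 reports for the parent antibody: "Twenty-six events were assessed as Grade 1, 29 events as Grade 2, 11 events as Grade 3, 2 events as Grade 4", plus one Grade 5.

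- Total: 26 + 29 + 11 + 2 + 1 = 69.
- Grade 1: 26/69 = 37.7%. Grade 2: 29/69 = 42.0%. Grade 3 or higher: 14/69 = 20.3%.

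Let f1 and f2 be the shares of Grade 1 and Grade 2 events managed without these drugs. The documents give neither, so both are assumed. Events lost = 26·f1 + 29·f2. The Grade 3 or higher share of flagged events = 14/(69 − lost).

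| f1 | f2 | Events lost | Grade 3 or higher among flagged |
|---|---|---|---|
| 0 | 0 | 0 (0%) | 14/69 = 20.3% |
| 0.5 | 0.25 | 20.25 (29.3%) | 14/48.75 = 28.7% |
| 1 | 0 | 26 (37.7%) | 14/43 = 32.6% |
| 1 | 0.5 | 40.5 (58.7%) | 14/28.5 = 49.1% |
| 1 | 1 | 55 (79.7%) | 14/14 = 100% |

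The last row is a ceiling. Table 5 itself excludes it for Grade 2 pneumonitis. These are shares of events, not of subjects, and they concern a different product.

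**The case against.** The case on the other side has real force, and it limits the point in five ways.

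- **Not all low-grade irAEs are lost.** A reader might infer that the SAP removes every one. It does not. The general rule allows moderate-dose steroids at Grade 1 to 2, persistent low-grade events are managed like Grade 3 to 4, and endocrine events on hormone therapy satisfy criterion 3. Protocol 3.4.2 also says investigators will be trained to give steroids early whenever an irAE is suspected. That sits uneasily with the Grade 1 rows of Table 5, and the two passages need reconciling; no view is taken here on which should govern.
- **Some examples may never be AEs.** Protocol 7.4.1.1 keeps laboratory and other investigational abnormalities out of AE reporting unless they bring signs or symptoms, lead to discontinuation or are judged medically important. Some Grade 1 liver elevations, asymptomatic TSH changes and radiographic-only pneumonitis will be excluded there and not by criterion 3.
- **The primary endpoints are not affected.** A reader might infer bias in the primary safety results. Protocol 8.3.1 lists DLTs, TEAEs and treatment-related AEs, none of which uses the irAE flag. Unflagged treatment-emergent events stay in the general TEAE tables and AE listings, although nothing in the tables marks them as immune-related. One qualification applies: under SAP 9.7 the general window ends 30 days after the last dose and the irAE window 90 days after, so an unflagged event with onset in between is left to the listings.
- **A subject-level size cannot be computed.** A reader might scale the parent antibody's 11.7% by the grade shares, to about 7.3% (Grade 1 lost) or 2.4% (Grades 1 and 2 lost). That assumes one event per subject, yet Protocol 3.4.2 reports 69 events against 56 + 4 = 60 cases. The 11.7% is 56/480 from the expansion part alone. The 69 were potential irAEs, 23 of them judged unrelated, so criterion 4 would remove some as well.
- **A specific definition is defensible.** Requiring treatment guards against calling every matching term immune-related. Dropping criterion 3 outright would let any matching term with a blank 4a answer count. The SAP also shows no investigator-reported irAE flag that could stand in for it.

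What stands is narrower: the restriction to treated events is not disclosed in the table titles, it depends on grade, and it does not match the protocol's definition or SAP 16.1.

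**Conclusion.** The point holds for low-grade irAEs that are reported as AEs and managed without corticosteroids, immunosuppressants or hormonal therapy. They are missing from the irAE summaries and from the irAE line of the ADA/nAb safety tables. The direction is clear: the irAE rate is understated and the grade distribution is shifted upward. The size is unknown because the documents do not give the share managed without these drugs. The parent-antibody grade mix shows only that low-grade events can be most of the total (55/69 = 79.7%). The conclusion rests on the wording of SAP 16.2.3.2 and on sites following Table 5. The more often sites give steroids on suspicion alone, the smaller the effect.

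**What to change.** In SAP 16.2.3.2:

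- Keep the four-criteria tables, and title them as irAEs treated with corticosteroid, immunosuppressant or hormonal therapy.
- Add one parallel set, any irAE and irAE by worst grade, using criteria 1, 2 and 4 without criterion 3. Show treated events as a subset row.
- In the parallel set, show events with missing criterion 4 entries on a separate line and do not count them as irAEs by default. Otherwise the missing-4a rule would over-count. This line also matters because the SAP does not say whether the etiology page was completed for untreated events.
- Reconcile the AESI description in SAP 16.1 with 16.2.3.2.

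The cost is one extra table set from eCRF fields the SAP already names, a somewhat higher reported irAE rate and some loss of specificity. SAP 6.1 records that the CSR and its addendum are approved and that no final analysis will follow, so the new tables would be post hoc and should be marked as such. They remain useful because SAP Section 4 foresees use of these analyses in submissions and manuscripts. If no table can be added, relabelling alone would make the restriction visible.
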